**Confidential Information**

**No use or disclose outside AbbVie is permitted without prior written authorization from AbbVie**

The Netherlands v 1.4 (26 March 2018). Protocol based on AbbVie shell protocol version 3.0 (22 April 2015) Page 28 of 65

The following will be documented:

- Laboratory data

Key clinical chemistry

- ALT
- AST
- $\gamma$ -GT
- Total bilirubin
- Albumin
- Creatinine

Remarks

including ULN  
including ULN,  
APRI and FIB-4, will be calculated

creatinine clearance will be calculated

Key hematology

- Hb
- Platelets
- Prothrombin time

or INR

Virology

- HCV RNA

quantitative/ qualitative HCV RNA PCR test, see 9.4.1.4

HIV-infected patients only

- CD 4 count
- HIV RNA

most recent assessment  
in copies/mL

- Tolerability (sAEs, see 11.1.4) and pregnancies (see 11.1.6)
- Patient questionnaires see 9.4.1.6

---

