**Table 2 - Data Documentation Schedule**

Assessment/ Procedure (only available data to be collected; no diagnostic or monitoring procedures to be applied to the patients apart from those of routine clinical practice)	Baseline	Treatment Period			Post-treatment (PT) Period		
		On-treatment visits	Mid treatment visit for pts receiving 24 weeks of therapy	EoT b	Early PT visit	SVR 12 visit	SVR 24 visit
Informed Consent	X a						
Demographic information	X						
Relevant CHC disease characteristics	X						
Liver fibrosis stage	X						
CHC treatment history	X						
HCV genotype and subtype	X						
HCV RNA samples	X	X	X	X	X	X	X
Clinical chemistry and hematology	X	X	X	X	X	X	X
ABBVIE REGIMEN initiation documentation c	X						
ABBVIE REGIMEN adherence		X	X	X			
Concomitant medication	X	X	X	X			
Relevant medical history, co-morbidities	X						
SAE, AE and pregnancy reporting	X	X	X	X	X d	X e	X e
For patients receiving RBV: Evidence, in accordance with local label, that female patient or female partner of male patient is not pregnant	X						
Health care resource utilization	X	X	X	X			
Patient questionnaires – WPAI, EQ5D-5L	X			X		X	X

Abbreviations: EoT = End of Treatment (at Week 12 or 24 or at premature discontinuation),

PT = Post-Treatment

- a Written informed consent must be obtained before any data documentation in the eCRF
- b Patients who prematurely discontinue should return to the site to document EoT data
- c Healthcare professional documents the type of therapy that will be initiated (12 vs 24 wks, Paritaprevir/r – ombitasvir alone vs Paritaprevir/r – ombitasvir + dasabuvir, with or without Ribavirine depending on the genotype of the virus and disease status of the patient)
- d Tolerability documentation until PT week 4
- e Pregnancy reporting for patients treated with DAA +/- RBV (see 11.1.6)

Confidential Information

No use or disclose outside AbbVie is permitted without prior written authorization from AbbVie  
 The Netherlands v 1.4 (26 March 2018). Protocol based on AbbVie shell protocol version 3.0 (22 April 2015) Page 30 of 65

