#### **9.4.1.5 Concomitant Medication**

**Concomitant medication** - the following will be documented:

- Concomitant medication used from the time when the decision is made to initiate treatment with the ABBVIE REGIMEN until after the last dose

It should be verified by the treating physician that concomitant medication can be safely administered with the ABBVIE REGIMEN (including ritonavir) and RBV. Some medications may be contra-indicated, some may require dose adjustments due to potential for drug-drug interactions (DDIs). The investigator or qualified designee should review the concomitant medication(s) labels and screen concomitant medications at each visit for potential DDIs.

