## **9.6 Data Management**

### **9.6.1 Electronic Case Report Forms**

Data for this study will be recorded in English by each participating center via an electronic data capture (EDC) system using a web-based eCRF. Examinations, diagnostic measures, laboratory assessments, findings and observations routinely performed in patients with CHC included in this cohort, will be transcribed by the investigator or designee from the source documents into the eCRF. Only data specified in the protocol will be entered into the eCRF. For each enrolled patient, the investigator or designee will create a new patient file in the eCRF and a unique patient number will be automatically allocated by the system.

A comprehensive data validation program utilizing front-end checks in the eCRF will validate the data. Automated checks for data consistency will be implemented; discrepancies need to be solved by the researcher in the eCRF before the module can be completed.

Follow-up on eCRF data for medical plausibility will be done by AbbVie personnel (or their representatives). Queries will be generated in the eCRF for online resolution at the site. The investigator or an authorized member of the investigator's staff will make any necessary data corrections to the eCRF. All change information, including the date and person performing the corrections, will be available via the audit trail, which is part of the EDC system. The principal investigator of each site will finally review the eCRFs for completeness and accuracy of available data and provide his or her electronic signature and date to the eCRFs as evidence thereof.

Access to the EDC system will be provided for the duration of the study through a password-protected method of internet access. Such access will be removed from investigator sites at the end of the site's participation in the study. Data from the EDC system will be archived on appropriate data media (e.g. CD-ROM) and provided to the investigator as a durable record of the site's eCRF data.

Original Questionnaires will be sent from the participating site to:

---

Confidential Information

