No data will be imputed for any effectiveness or safety analyses except for the analyses of the HCV RNA endpoints. When there is no HCV RNA value in a visit time window post-baseline, but prior to EoT, the closest values before and after the window, regardless of the value chosen for the subsequent and preceding window, will be used for the flanking imputation described below. If a patient has a missing HCV RNA value at a post-baseline visit prior to EoT but has undetectable HCV RNA (with LLoD  $\leq 50$  IU/mL) or unquantifiable, but detectable HCV RNA levels (with LLoQ  $\leq 50$  IU/mL) at both the preceding and succeeding measurements, the HCV RNA level will be considered undetectable or unquantifiable, respectively, at this visit for this patient. In addition, if a patient has an unquantifiable HCV RNA level at the preceding measurement and an undetectable HCV RNA level at the succeeding measurement, or vice versa, the HCV RNA level will be imputed as unquantifiable at this visit for this patient. For virological response at EoT a corresponding backward imputation approach will be applied. This means if HCV RNA is missing at EoT, then unquantifiable or undetectable will be assumed for EoT, if the succeeding HCV RNA value is undetectable or unquantifiable. For SVR12 the single last available HCV RNA measurement  $\geq 70$  days post-treatment will be used. Subsequent to this flanking and backward imputation, if the HCV RNA value remains missing at a specific time point, then the patients will be considered as virological failure at this time point (i.e. not undetectable or unquantifiable).

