4.2.3 Handling of missing data

No data will be imputed for any effectiveness or safety analyses except for the analyses of the HCV RNA endpoints and certain PRO endpoints. The discussion of missing data imputation for the PRO endpoints is included in section 4.2.7.2.2.

HCV RNA values will be selected for an RVR, EOTR and SVR analysis based on visit windows as defined in Table 2. When there is no HCV RNA value in a visit window based on defined visit windows, the closest values before and after the window, regardless of the value chosen for the subsequent and preceding window, will be used for the flanking imputation described below. For

analysis of RVR, EOT and SVR, if a subject has a missing HCV RNA value at a post-Day 1 visit but with undetectable or unquantifiable (LLoD or LLoQ \leq 50 IU/mL) HCV RNA levels at both the preceding value and succeeding value, the HCV RNA level will be considered undetectable or unquantifiable, respectively, at this visit for this subject. In addition, if a subject has an unquantifiable HCV RNA level at the preceding value and an undetectable HCV RNA level at the succeeding value, or vice versa, the HCV RNA level will be imputed as unquantifiable at this visit for this subject.

For analyses of RVR, subjects still missing a value for the visit after flanking imputation will be considered as a failure. For EoTR and SVR analysis, if there is no value in the appropriate window after flanking imputation but there is an HCV RNA value after the window, then it will be imputed into the EoTR or SVR window respectively. Subsequent to this flanking and backward imputation, if the HCV RNA value remains missing at a specific time point, then the subject will be considered as virological failure at this time point (i.e., not undetectable or unquantifiable).

If a subject starts another treatment for HCV, then all HCV RNA values for this subject measured on or after the start date of the new HCV treatment will be excluded from analyses. The subject will be considered a failure for summaries of viral response at all time points after the start of the new HCV treatment.

Due to the non-interventional nature of this study several different methods for determination of the HCV RNA value can be applied. For the purpose of the statistical analysis, a HCV RNA measurement is considered <50 IU/mL,

- if a PCR test was used

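### The SAP scores patients who start another HCV treatment as failures, but neither document specifies recording that start date after end of treatment, so on-retreatment values may count as SVR24 and, by a narrower route, as SVR12

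*SAP*

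**What the plan says.** SAP 4.2.3 has a two-part rule for a patient who begins another HCV treatment. First, "all HCV RNA values for this subject measured on or after the start date of the new HCV treatment will be excluded from analyses". Second, "The subject will be considered a failure for summaries of viral response at all time points after the start of the new HCV treatment". Both parts depend on a dated record of the new treatment.

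The protocol's medication item (9.4.1.5) is limited to "Concomitant medication used from the time when the decision is made to initiate treatment with the ABBVIE REGIMEN until after the last dose". The row in Protocol Table 2 is "Concomitant medication X X X X": four marks, at baseline, on-treatment, mid-treatment and EoT. The early post-treatment, SVR12 and SVR24 columns are empty, and SAP Table 1 has the same row. Protocol 9.4.1.3 lists what is documented after treatment: laboratory data including HCV RNA, tolerability and pregnancies, and questionnaires. Protocol 9.6.1 adds: "Only data specified in the protocol will be entered into the eCRF".

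HCV RNA itself is recorded through the SVR24 visit, and both documents require every measurement to be entered. When an SVR window is empty and flanking imputation does not fill it, SAP 4.2.3 looks later: "but there is an HCV RNA value after the window, then it will be imputed into the EoTR or SVR window respectively".

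**The concern.** The SAP has already decided that response reached on another HCV treatment does not belong to this regimen. If the start date is missing from the database, that decision cannot be applied to treatment begun after EoT, and the ordinary window rules take over. Those rules look only at HCV RNA and days since the last ABBVIE REGIMEN dose.

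The patients affected would be those who relapsed or stopped early, since they are the ones with a reason to be retreated. Any resulting error in an SVR rate therefore runs upward. With 50-55 patients and few expected failures, one or two such patients would be visible in the reported rate.

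**Working it through.** The documents state no figure on this point, so the check is mainly a trace of the rule's input through the collection lists and then through the SAP's own steps.

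**1. Where could the start date come from?**

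| Place | What it covers | Gives a post-EoT HCV treatment date? |
|---|---|---|
| Protocol 9.4.1.1 | Prior HCV therapy, at inclusion | No |
| Protocol 9.4.1.5, Table 2; SAP Table 1 | Medication up to around the last dose, recorded up to EoT | Only for a switch made around the last dose |
| Protocol 9.4.1.3 | Laboratory data, tolerability and pregnancies, questionnaires | No |
| SAP 4.2.8.2 | Profile B is an earlier drug resumed after treatment; profile D is a drug begun during treatment | No profile for a drug first begun after treatment |
| SAP 4.2.5 | Reasons for not completing the study, including relapse | No treatment name or date |

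No listed source specifies the date for treatment begun after EoT.

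**2. SVR24.** SAP 4.1.2 defines it as HCV RNA below 50 IU/mL 24 weeks after EoT; SAP Table 2 sets the window at days 127-210. It is not conditional on SVR12 or on absence of other therapy. A patient who relapses by week 12, is retreated, and is below 50 IU/mL at day 200 meets it directly. Having a value after day 126, the patient is also in the SVR24 version of the core population with sufficient follow-up, where SVR24 is reported.

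**3. SVR12.** The SAP window is days 70-126. There are two routes:

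- Retreatment starts early enough that the value in the window is already below 50 IU/mL.
- The window is empty. Take EoT below 50, day 40 at or above 50, nothing on days 70-126, and day 200 undetectable on retreatment. Flanking imputation needs both neighbours undetectable or unquantifiable; day 40 is neither, so it does not apply. Backward imputation then places the day-200 value in the SVR12 window, and the patient is an SVR12 success despite the day-40 value.

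**4. Relapse output.** SAP 4.2.7.2.1 estimates relapse in completers with EoT response, and admits patients who failed between EoT and day 70. The patient in step 3 satisfies this, so could be an SVR12 responder in one table and a relapse in another.

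**5. Size.** Inputs: N = 50-55 (SAP 3.2); Wilson 95% intervals (SAP 4.2.7.1); SVR of 92% and 96% in the cirrhosis trial cited in Protocol 7.1, used only for scale. All enrolled patients are assumed to be in the core population.

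- One patient: 1/50 = 2.0 points; 1/55 = 1.8 points.
- Expected failures at 4-8%: 0.04 × 50 = 2.0 to 0.08 × 50 = 4.0; 0.04 × 55 = 2.2 to 0.08 × 55 = 4.4. One misclassified patient among 2 to 4 failures removes a half to a quarter of them.
- Wilson interval: [p + z²/2n ± z√(p(1−p)/n + z²/4n²)] / (1 + z²/n), z = 1.96. For 48/50, the centre is (0.96 + 0.0384)/1.0768 = 0.927 and the half-width is 1.96 × √(0.000768 + 0.000384)/1.0768 = 0.062, giving 86.5-98.9%.

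| True failures | Rule applied | One retreated failure counted as responder |
|---|---|---|
| 2 of 50 | 48/50 = 96.0% (86.5-98.9) | 49/50 = 98.0% (89.5-99.6) |
| 4 of 50 | 46/50 = 92.0% (81.2-96.8) | 47/50 = 94.0% (83.8-97.9) |
| 2 of 55 | 53/55 = 96.4% (87.7-99.0) | 54/55 = 98.2% (90.4-99.7) |
| 4 of 55 | 51/55 = 92.7% (82.7-97.1) | 52/55 = 94.5% (85.1-98.1) |

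The failure counts and the single retreated patient are assumptions. A smaller denominator, as is possible for SVR24, makes each step larger.

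**The case against.** A reader might infer that the SAP rule cannot run at all. The documents do not show that. The eCRF is not included, and it evidently holds items that the protocol's lists do not name: reasons for not completing the study (SAP 4.2.5), alcohol consumption (SAP 4.2.6.4), and a report of relapse separate from the HCV RNA result (Protocol 9.7.1). A retreatment field could exist despite Protocol 9.6.1. A switch around the last dose may also appear as concomitant medication, since recording includes EoT and early discontinuers are asked to return for that visit. What stands is that the date is unspecified for treatment begun after EoT.

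A reader might also infer that relapses are hidden. They need not be: the relapse analysis keeps failures between EoT and day 70. The consequence is outputs that could conflict.

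Nor should the SVR12 exposure be overstated. If the only value on days 70-126 is at or above 50 IU/mL, the patient is a failure and nothing is imputed. The protocol's selection rule, "For SVR12 the single last available HCV RNA measurement" from day 70 with no upper limit, would be more exposed, but SAP 4.1.1 openly replaces it with an upper bound of 126 days. Backward imputation reopens that bound only when the window is empty. SAP 4.2.7.2.1 also reports response among completers, which leaves out early stoppers, though the primary analysis covers the whole core population.

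Finally, the study is descriptive with no hypothesis test, and no retreatment frequency is given. Both points limit how much weight the size can carry; neither supplies the missing date.

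**Conclusion.** The concern holds as a gap in specification. SAP 4.2.3 relies on a date that neither document says will be collected after EoT. Unless the eCRF holds it, on-retreatment values can count as SVR24, mainly, and as SVR12 through the two routes traced above. The empty-window route is a weakness of the imputation text itself: as written, without a retreatment date, it overrides a recorded post-EoT value of at least 50 IU/mL.

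The error can only raise the SVR rates, by 1.8 to 2.0 points per patient if 50-55 patients are analysed. Whether it occurs at all depends on two things the documents do not show: the eCRF content and how many patients are retreated within follow-up. The table above gives ranges under assumptions and is not a forecast.

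**What to change.** 1. Confirm that the eCRF records the name and start date of any HCV treatment begun after the last ABBVIE REGIMEN dose. If it does not, query sites from charts before database lock, at least for patients with HCV RNA of 50 IU/mL or more at or after EoT and for those who discontinued early. The protocol version is dated 26 March 2018 and data collection ends in April 2018, so a retrospective query is more realistic than a new visit item.
2. Add to SAP 4.2.3: a value after an SVR window is not imputed back if any HCV RNA of 50 IU/mL or more was recorded between EoT and that value; the patient is then a failure for that window. This needs no new data.
3. Add: where virological failure is documented but no retreatment date can be obtained, the patient is a failure at later SVR time points.

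The cost is one query per affected patient and two SAP sentences. The reported SVR rate may be slightly lower. Items 2 and 3 are conservative: a patient who had such a value and cleared without retreatment could also be scored as a failure, so any patient classified this way should be listed.

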4.2.4 Site and Researcher Information

Data of the study sites and of the Researcher will be presented in summary tables.

The summary tables for site information will show absolute and relative frequencies for the institution type (private practice/ private hospital, general hospital, academic/ university hospital, other), the type of unit (general population, transplant, drug user, HIV/ HCV co-infection, hepatocellular carcinoma [HCC]), and the site location (urban, rural). Regarding type of unit multiple answers per site are possible.

The principle researcher experience will be summarized by presenting for each therapeutic specialty (hepatology, infectious disease, gastroenterology, internal medicine, transplant, general practitioner) the number and percentage of principle researchers, who have the specific experience. Furthermore, the number and percentage of sites with at least one researcher (i.e. including co-researcher) of the therapeutic specialty concerned and the number of HCV-infected patients typically seen per month at the site (<25, 25-50, 51-75, 76-100, >100), including the patients seen by co-researcher, will be summarized. Note: Multiple therapeutic specialties could be reported per researcher.

An overview of Tables for site and researcher information is given in Table 4.

Table 4 Overview of Outputs for Site and Researcher Information

Output Title	Output Short Name	Analysis Population
Site Information - <country>	tsi_<c>	Sites with patients
Researcher Experience- <country>	tre_<c>	Sites with patients

The layouts of the tables mentioned above are provided in Part II of the SAP (Table Shells).

4.2.5 Patient Disposition

The frequencies of patients belonging to the different populations (i.e. EP, TP, CP, CPSFU; SP) will be summarized by genotype and cirrhosis status and overall using the EP analysis groups as specified in section 4.2.1. The reasons for exclusion from a particular population will be also summarized in the frequency tables. Additionally, information on patient disposition will be listed.

Furthermore the frequency of patients not completing the study as defined per protocol (i.e. no HCV RNA assessment performed at least 10 weeks post-treatment), will be summarized by treatment regimen and cirrhosis status and additionally by genotype and cirrhosis status and overall for the SP and CP. The reasons for not completing the study as entered on the CRF will be displayed (i.e. failure to return, insufficient virological response (HCV RNA detectable at end of treatment, relapse post-treatment), patient never started treatment, withdrawn consent, death, other).

Additionally, the main reason for early termination of the ABBVIE regimen (AE or SAE [Physician decision], virological non-response [Physician decision], rebound or breakthrough [Physician decision], resistance to DAA [Physician decision], patient refused to continue treatment, patient withdrew consent to participate in the study, lost to follow-up, other, unknown [if actual duration is shortened for more than 7 days]) and Ribavirin (Anemia, Nausea/Vomiting, Rash, Other) will be summarized by treatment regimen and cirrhosis status and additionally by genotype and cirrhosis status and overall for the following different analysis populations: CP and SP.

Finally the study regimens assigned at baseline will be summarized (a) by genotype and cirrhosis status and (b) by genotype and pre-treatment status (treatment naïve vs treatment experienced) for CP and SP.

An overview of Tables is given in Table 5.

Table 5 Overview of Outputs for Patient Disposition

Output Title	Output Short Name	Analysis Population
Patient Disposition by Genotype and Cirrhosis Status – EP - <country>	tdis_<c>_gc_ep	Patients Enrolled
Listing of Patient Disposition - EP- <country>	ldis_<c>_ep	Patients Enrolled
Premature Termination of the Study and its Main Reason by <Treatment Regimen/ Genotype> and Cirrhosis Status - CP - <country>	tps_<c>_<t/g>c_cp	Core population
Premature Termination of the Study and its Main Reason by <Treatment Regimen/ Genotype> and Cirrhosis Status - SP - <country>	tps_<c>_<t/g>c_sp	Safety population
Premature Termination of Treatment and its Main Reason by <Treatment Regimen/ Genotype> and Cirrhosis Status - CP - <country>	tpt_<c>_<t/g>c_cp	Core population
Premature Termination of Treatment and its Main Reason by <Treatment Regimen/ Genotype> and Cirrhosis Status - SP- <country>	tpt_<c>_<t/g>c_sp	Safety population
Treatment Regimen by Genotype and Cirrhosis Status - CP - <country>	ttr_<c>_gc_cp	Core population
Treatment Regimen by Genotype and Cirrhosis Status - SP - <country>	ttr_<c>_gc_sp	Safety population
Treatment Regimen by Genotype and Pretreatment Status - CP - <country>	ttr_<c>_gpe_cp	Core population
Treatment Regimen by Genotype and Pretreatment Status - SP - <country>	ttr_<c>_gpe_sp	Safety population

The layouts of the tables mentioned above are provided in Part II of the SAP (Table Shells).

